3.2.2 Stage 2 Design

In Stage 2, we will randomize the primary care providers at Atrius Health who were assigned to usual care in Stage 1 in equal proportions to up to one of the 5 most promising treatment arms or to continue to receive usual care. We will also randomize any additional providers who prescribed at least one eligible anticholinergic to at least one older adult in the 180 days prior to randomization for secondary analyses. Providers randomized to one of the 5 selected treatment arms will receive an EHR tool to guide their care of eligible patients. As in Stage 1, we will randomize providers based on demographic characteristics, patient case-mix factors, and

baseline rates of high-risk medication prescribing. Patient eligibility will be identical to that used in Stage 1 except patients will also be included if they had been prescribed at least 90 pills of eligible anticholinergics in the last 180 days. Follow-up in Stage 2 will last at least 8 months, until enough data points have accrued.

3.2.3 Replication Trial Design

[figure not shown]
This replication trial is a cluster-randomized, NIH-defined Phase III pragmatic trial. The study statistician, in partnership with data analysts at MGB, will generate and implement the randomization scheme, with oversight by the Principal Investigators. All the study sites will be at MGH for this trial; we have received approval from leadership at MGH primary care practices and Digital Health eCare teams to conduct this trial. For study evaluation, data regarding patients' medical history, disease control, medication use, and healthcare utilization will be obtained from EHR data or administrative claims data. The administrative claims data used for evaluation in this study will come directly from MGB in HIPAA-limited datasets through their risk-bearing contracts, as applicable.

We plan to randomize primary care providers at MGH to one of the 2 most promising treatment arms identified in the adaptive randomized trial conducted at Atrius Health or usual care. We expect to randomize approximately 200 providers. Providers randomized to one of the 2 selected treatment arms will receive an EHR tool to guide their care of eligible patients. If the adaptive trial does not demonstrate the superiority of any EHR tools over usual care, we will select the two statistically most promising of the arms for this parallel group trial. We will randomize providers based on provider demographic characteristics, patient case-mix factors, and baseline rates of high-risk medication prescribing measured in EHR data.

[figure not shown]
Providers will be eligible if they prescribed a benzodiazepine, sedative hypnotic, or two distinct anticholinergics to at least one older adult in the 180 days prior to randomization. Providers will receive these EHR tools for their patients who meet the following criteria: 1) older adults (aged 65 years or more), and 2) who have been prescribed at least 90 pills of benzodiazepine or sedative hypnotic or have been prescribed at least one active orders of at least 90 pills of two different anticholinergics in the last 180 days. Follow-up will last 12 months. These patients will also be included in the analyses. The type and timing of EHR tool that the providers receive for these patients will vary based on their assigned intervention arm.

3.3 Study Schema

3.3.1 Atrius (Adaptive Trial)

3.3.2 Mass General Brigham (Replication Trial)

3.4 Scientific rationale for study design

Because there are numerous ways in which these EHR tools could be designed using behavioral principles, we propose a randomized adaptive design at Atrius Health that will increase statistical efficacy followed by a replication trial at MGH.^{16,17} This adaptive method has been used to improve the efficiency of traditional trials.¹⁶⁻²⁰ We propose to sequentially modify (i.e., adapt) the EHR tools that are presented to providers in the intervention groups based on identifying the tools that are the least and most successful at reducing inappropriate prescribing. This approach is highly feasible in the current context since the outcome on the basis of which intervention adaptation will occur (i.e., inappropriate prescribing) will be almost immediately observable using EHR data. This MGB replication trial will explicitly test replicability and scalability by replicating the trial at another distinct study site than the Atrius Health adaptive trial that we will first conduct. Further, the use of a randomized trial in this setting is scientifically justified, as this design will be able to provide evidence of causality in the effectiveness of the tools on reducing prescribing and rates of clinical outcomes. This replication trial was also part of the specific aims submitted and approved by the NIH. Further, the use of a randomized trial in this setting is scientifically justified, as this design will be able to provide evidence of causality in the effectiveness of the tools on reducing prescribing and rates of clinical outcomes. An observational study design, by contrast, would not provide the same degree of scientific rigor.

3.5 Justification for intervention

The focus areas for the EHR tools will be primarily drawn from the outpatient Choosing Wisely recommendations in geriatric medicine but are also informed by the Beers Criteria and other major clinical guidelines.²¹⁻²³ In specific, we plan to focus on the following therapeutic classes: (1) benzodiazepines; (2) sedative hypnotics (sleep medicines) and (3) anticholinergics. These classes were chosen because they all have established clinical guidelines recommending reductions in use, continue to be heavily over-prescribed, contribute significantly to poor clinical

outcomes in older adults, and also have non-drug or less risky therapeutic alternatives. While prescribing non-drug options may be the optimal alternative to these potentially inappropriate medications, their adverse effects could also be attenuated by choosing alternative medications in a different drug class, lower doses of medication, or alternative, safer medications within the same drug class.

We have chosen to focus on key principles of behavioral economics and cognitive psychology to “nudge” providers to optimize prescribing, including timing, salience, framing, simplification, cold state outreach, pre-commitment, and boosting. These principles were selected based on their effectiveness in other settings²⁴⁻²⁷, their applicability to the care of older adults, and their ability to be adapted to the EHR context.

3.6 End-of-study definition

The adaptive trial will be completed approximately 8 months after Stage 2 randomization. Providers and their eligible patients will be followed until the end of this follow-up date, or until censoring.

The replication trial will be completed 12 months after randomization. Providers and their eligible patients will be followed until the end of this follow-up date, or until censoring.

3.7 Data sources

We will use EHR data to implement the EHR tools, identify study subjects, track study progress, and evaluate the effect of the interventions. We will also use administrative claims data to evaluate tertiary outcomes among the subgroup of patients with claims data.

The Atrius data warehouses reside in an Oracle environment and consist of the Clarity and Payer databases. The Clarity database is a relational database that contains clinical and financial information from the Epic Suite of products; including the electronic medical record system, the appointment scheduling system, the patient accounting system, and the master

patient index (Identity). The various tables within the Clarity database are refreshed on a daily, weekly or monthly basis.

For the claims data, the Medicare claims data are being provided by the funder, the National Institute on Aging (NIA), through their partnership with Acumen and the established MedRIC (<https://www.medric.info/data-enclave/data-pages/data>). In order to obtain claims data from the funder, we will provide them with Medicare Beneficiary Identifier (MBI) for linked patients in our study. We are executing all appropriate data use agreements with the NIA and Acumen to receive these data. The claims data will be available for linked patients in our study.

At MGB, we will extract clinical information from the electronic medical record system via the Epic Enterprise Data Warehouse (EDW) or the Mass General Brigham Research Patient Data Registry (RPDR). Accessing the EDW in particular is necessary in order to adequately identify and link all eligible patients seen by the enrolled providers in our study and measure outcomes, which is not possible using other sources.

3.8 Schedule of activities

Data collection	Stage 1: Pre-randomization	Stage 1: Follow-up	Stage 2: Pre-randomization	Stage 2: Follow-up	Replication: Pre-randomization	Replication: Follow-up
EHR review for provider eligibility	X		X		X	
Patient characteristics (Demographics, clinical characteristics)	X		X		X	
Provider characteristics (Demographics, patient case-mix)	X		X		X	
Benzodiazepine/sedative hypnotic prescribing		X		X		X
Benzodiazepine/sedative hypnotic dispensations				X		X
Anticholinergic prescribing/dispensations				X		X
Adverse drug events		X		X		X
Falls or fractures				X		X
Resource use (hospitalizations, ER visits)				X		X

4. Study Population

The study will intervene upon primary care providers (primary care provider designated physicians, nurse practitioners, physician assistants) and their patients in the outpatient practices of Atrius Health and Mass General Hospital.

4.1 Inclusion Criteria

The study will include provider and patient subjects. Limited inclusion criteria will be applied to maximize generalizability in accordance with pragmatic trial principles by PRECIS-2 (PRagmatic Explanatory Continuum Indicator Summary).²⁸ The study criteria are defined below.

Stage 1

Providers will be eligible for this Stage of the trial if they:

- are a primary care provider at Atrius Health
- prescribed a benzodiazepine or sedative hypnotic to at least one older adult (aged 65 years or more) in the prior 180 days

Patients will be included for this Stage of the trial if they:

- are the primary care patient of an eligible provider
- are aged 65 years or more
- have been prescribed at least 90 pills of benzodiazepine or sedative hypnotic in the prior 180 days

Stage 2

Providers will be eligible for this Stage of the trial if they:

- are a primary care provider at Atrius Health
- prescribed a benzodiazepine, sedative hypnotic, or anticholinergic to at least one older adult in the 180 days prior to randomization

Patients will be included for this Stage of the trial if they:

- are the primary care patient of an eligible provider
- are aged 65 years or more
- have been prescribed at least 90 pills of benzodiazepine or sedative hypnotic or at least 90 pills of an eligible anticholinergic in the prior 180 days

Replication

The subjects involved in this trial are providers from multiple clinical sites, all at Mass General Hospital. The target population of providers and the patients they treat is pragmatic and widely representative. Providers will be eligible if they treat older adult patients. Each study clinic has an EHR system in place. The inclusion criteria are limited to maximize generalizability in accordance with pragmatic trial principles by PRECIS-2 (PRagmatic Explanatory Continuum Indicator Summary).

Providers will be eligible if they:

- Are a primary care provider at Mass General Hospital, with a minimum clinical schedule of 2 sessions per week
- Prescribed a benzodiazepine, sedative hypnotic, or anticholinergic to at least one older adult in the 180 days prior to randomization

Patients will be included if they:

- Are assigned to one of the randomized primary care providers (by MGB indicators)
- Are aged 65 years or more

- Have been prescribed at least 90 pills of benzodiazepine or sedative hypnotic or at least one active orders of at least 90 pills of two different anticholinergics in the prior 180 days

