The prescribing of inappropriate medications for older adults is extremely common in the United States, ranging from 12% in community settings to 40% of those who are institutionalized.¹⁻³ Benzodiazepines, anticholinergics, and sedative hypnotics are among the most commonly prescribed in circumstances that are inconsistent with practice guidelines.^{3,4} While inappropriate prescribing increases the risk of adverse health consequences for all patients, older adults are particularly vulnerable.^{2,5-7} Physicians' lack of awareness of alternatives, ambiguous practice guidelines, and perceived pressure of patients or caregivers are among the reasons why these drugs are used more than might be optimal.²

Reducing inappropriate use of these drugs may be achieved through decision support tools for physicians that are embedded in electronic health record (EHR) systems. While EHR strategies are widely used to support the informational needs of providers, these tools have demonstrated only modest effectiveness at improving prescribing.⁸⁻¹³ The moderate effectiveness of current clinical decision support tools is thought to be largely due to what content they contain and the lack of provider-focused design principles being used to develop them.^{14,15} Prior approaches have also been criticized for the sheer volume of alerts, the lack of clinical significance of the tools, and the poor/delayed timing of the clinical decision support (i.e., after the prescribing decision). Accordingly, the effectiveness of these tools could be enhanced by leveraging recently-gained insights from behavioral economics and other related sciences. Their application to EHRs has been limited, and they have not been used to reduce the prescribing of potentially harmful medications to older adults.

2. Study Aims

The overall goal of the proposed research is to evaluate whether EHR-based tools, optimized using behavioral science principles, reduce inappropriate prescribing among older adults. Our overall hypothesis is that thoughtful incorporation of behavioral principles into

EHRs will reduce inappropriate prescribing and adverse drug events among older adults compared to usual care.

The objectives and endpoints for the adaptive and replication trials are summarized below.

OBJECTIVES	ENDPOINTS	JUSTIFICATION FOR ENDPOINTS
Primary		

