To determine whether EHR-tools designed using behavioral science principles are more effective than at reducing inappropriate prescribing of high-risk medications in older adults than standard EHR tools or usual care.	Composite of 1) discontinuation of high-risk medications (benzodiazepines, sedative hypnotics, or anticholinergics [in secondary analyses]) or 2) ordering a gradual dose taper for one of these medications	These outcomes are rapidly measurable using EHR data alone and will provide evidence of provider behavior change.
Secondary		
To examine whether behavioral science-based EHR tools reduce cumulative prescribing of high-risk medications in older adults compared with usual care.	Quantity of high-risk medication prescribed, defined by number of milligram equivalents of high-risk medications prescribed to patients in follow-up	These outcomes capture the extent to which high-risk medications are cumulatively prescribed to patients by all Atrius providers over the follow-up period.
Tertiary/Exploratory		
To evaluate whether behavioral science-based EHR tools reduce the risk of clinically-significant adverse drug events, falls, fractures, hospitalizations, or emergency room visits compared with usual care.	Rates of adverse drug events, falls, fractures, hospitalizations, and emergency room visits in follow-up; quantity of high-risk medications dispensed to patients in follow-up period	These outcomes measure clinical outcomes that are consequences of these high-risk medications, measured in medical and pharmacy administrative claims data.

3. Study Design

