4.2 Exclusion Criteria

Patients not meeting the inclusion criteria above will not be included in the study. No other exclusion criteria will be used.

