6.2 Outcomes

For both Stages, the primary outcome will be a binary composite measure of a reduction in inappropriate prescribing, evaluated using EHR data from Atrius Health. In specific, we will measure a composite of 1) discontinuation of high-risk medications (benzodiazepines, sedative hypnotics, or anticholinergics [included in secondary analyses]), defined by either: a) active discontinuation and no subsequent order or b) no order during follow-up or 2) ordering a gradual dose taper (for benzodiazepine or sedative hypnotics). If either of these actions is taken by the provider for a specific patient at any point in the follow-up window, we will classify the patient as having had a reduction in inappropriate prescribing. If the patient has multiple therapeutic classes of interest (e.g., benzodiazepines and sedative hypnotics), we will classify patients with a reduction for any class as a “reduction” for the composite measure. In secondary analyses, we will include anticholinergics. We will also stratify patients by their number of eligible therapeutic classes (i.e., one, two, or three classes) and analyze outcomes within these strata.

In Stage 2 and the replication trial, secondary outcomes include the quantity of high-risk medication prescribed, defined by number of milligram equivalents of high-risk medications prescribed to patients in the follow-up period to capture cumulative prescribing by all providers

at Atrius Health. As above, we will also stratify patients by their number of eligible therapeutic classes (i.e., one, two, or three classes) and analyze outcomes within these strata.

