Because this is a randomized trial, our primary analyses are planned as unadjusted; in secondary analyses, we will adjust for patient age, race/ethnicity, and gender.. Given the nature of the data and how the outcomes are categorized, there will not be missing values for the primary endpoint, as the absence of action is classified as no action by the provider. For the primary analysis, we will include all eligible patients in the denominator who had at least one in-person or telehealth visit with their primary care provider. In secondary analyses, we will

include all eligible patients of those primary care providers in the denominator, regardless of whether the patient visited the provider over the follow-up period.

7.3.1b Replication trial

All analyses will use intention-to-treat principles. We will use generalized estimating equations to adjust for clustering and repeated observations. For the inappropriate prescribing outcome, we will use a log link function and binary distributed errors. For the adverse clinical outcomes, we will use a log link function and binary distributed errors. These models generate the estimated relative risks (RRs) with robust standard errors and are considered to be particularly appropriate when outcomes are common (e.g., incidences of $\geq 10\%$). Because this is a randomized trial, our primary analyses are planned as unadjusted; however, in secondary analyses, we will adjust for patient age, race/ethnicity, and gender.

Given the nature of the data and how the outcomes are categorized, there will not be missing values for the primary endpoint, as the absence of action is classified as no action by the provider. For the primary analysis, we will include all eligible patients in the denominator who had at least one visit with their primary care provider. In secondary analyses, we will include all eligible patients of those primary care providers in the denominator, regardless of whether the patient visited the provider over the follow-up period.

7.3.2 *Analysis of secondary endpoints*

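### Replication patients who qualify on anticholinergics alone enter the primary denominator, but the primary endpoint counts no drug they could stop

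*Combined protocol and SAP*

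**What the plan says.** - **Eligibility.** Section 4.1 (Replication) admits patients with at least 90 pills of a benzodiazepine or sedative hypnotic or, as an alternative that is sufficient alone, "at least one active orders of at least 90 pills of two different anticholinergics in the prior 180 days". Section 3.2.3 gives the same two routes and adds: "These patients will also be included in the analyses".
- **Exclusions.** Section 4.2: "No other exclusion criteria will be used".
- **Primary denominator.** Section 7.3.1b: "For the primary analysis, we will include all eligible patients in the denominator who had at least one visit with their primary care provider". There is no limit by drug class. Section 7.3.1a defers anticholinergics to secondary analyses; 7.3.1b has no such sentence.
- **Primary endpoint.** Section 2 introduces its table with "The objectives and endpoints for the adaptive and replication trials are summarized below". The primary row lists discontinuation of benzodiazepines, sedative hypnotics or, with a bracketed limit, "anticholinergics [in secondary analyses".
- **Scoring.** In section 6.2 one way to meet discontinuation is "b) no order during follow-up", and the taper limb applies only to benzodiazepines and sedative hypnotics. Section 7.3.1b says that where nothing is done, the patient is classed as having had no action by the provider.

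**The concern.** Read together, these rules put anticholinergic-only patients in the replication primary analysis although the primary endpoint counts no drug that they take. Their primary outcome is fixed by a scoring convention and is largely the same in every arm, so they carry almost no information on the primary question. The plan supplies two conventions that point in opposite directions, and two analysts following the text could report different primary results from the same data. At stake are the size of the primary difference, the power claimed in section 7.2 and, under one convention, the relative risk that the model in 7.3.1b estimates.

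**Working it through.** **Plan's own figure.** Section 7.2 claims more than 80% power for an absolute difference of 10 points or smaller, with intra-provider correlation 0.1 and a Holm-Bonferroni correction. The usual-care rate and cluster size for the replication are not given, so the figure cannot be reproduced, only bracketed. Inputs: about 200 providers (3.2.3) in three equal arms, K = 200/3 = 66.7 per arm; two-sided alpha 0.025, the first Holm step for two comparisons if overall alpha is 0.05 (stated only for the adaptive trial). Effective patients per arm are K·m/(1 + (m − 1)·0.1). Power for +10 points, pooled two-proportion formula:

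| Patients per provider, m | Effective n | p0 = 5% | 10% | 20% | 30% | 45% |
|---|---|---|---|---|---|---|
| 20 | 459.8 | 99.8% | 97.9% | 89.8% | 82.7% | 78.7% |
| 10 | 350.9 | 98.6% | 93.1% | 79.5% | 70.5% | 65.9% |
| 5 | 238.1 | 92.2% | 79.5% | 61.0% | 51.9% | 47.6% |

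The claim is attainable for some inputs but cannot be confirmed.

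**Effect of anticholinergic-only patients.** Let f be their share of the denominator, and p0 and p1 the success rates in the other patients.

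- Scored as successes: rates f + (1 − f)p0 and f + (1 − f)p1.
- Scored as failures: rates (1 − f)p0 and (1 − f)p1.
- In both cases the difference is (1 − f)(p1 − p0). The ratio stays p1/p0 under failure scoring and moves toward 1 under success scoring.

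**Power.** Assumptions: m = 20 (stated only for the adaptive trial), p0 = 20%, p1 = 30%, correlation 0.1 among benzodiazepine/sedative-hypnotic patients, and anticholinergic-only status independent of provider. Patients with a fixed outcome add no between-provider variation, so within-provider covariance is (1 − f)²·0.1·p(1 − p). With q the mixed rate, variance per arm is [q(1 − q) + (m − 1)·covariance]/(K·m), and power is Φ(difference/SE − 2.241).

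Worked case f = 25%: covariance is 0.5625 × 0.016 = 0.0090 (usual care) and 0.5625 × 0.021 = 0.0118 (active); K·m = 1333.

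- Successes: 40% v 47.5%. Variances (0.240 + 19 × 0.0090)/1333 = 0.000308 and (0.249 + 19 × 0.0118)/1333 = 0.000355; SE 0.0258; 0.075/0.0258 − 2.241 = 0.67; power 75%.
- Failures: 15% v 22.5%. Variances 0.000224 and 0.000299; SE 0.0229; power 85%.
- Restricted, m = 15: 20% v 30%. Variances 0.000384 and 0.000504; SE 0.0298; power 87%.

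| f | Difference | Success scoring: power (RR) | Failure scoring: power (RR) | Restricted: power (RR) |
|---|---|---|---|---|
| 0 | 10 points | 90% (1.50) | 90% (1.50) | 90% (1.50) |
| 10% | 9 points | 85% (1.32) | 88% (1.50) | 89% (1.50) |
| 25% | 7.5 points | 75% (1.19) | 85% (1.50) | 87% (1.50) |
| 50% | 5 points | 51% (1.08) | 75% (1.50) | 80% (1.50) |

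The last column is the difference of 10 points in the restricted set. At p0 = 5%, the only rate in the documents (adaptive trial), failure scoring keeps 98% power even at f = 50%. Success scoring there gives 56%, and at f = 25% it turns a relative risk of 3.0 into 1.26.

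**The case against.** Two coherent readings would remove the problem. In the first, anticholinergics count in the replication primary outcome: the detailed definition in 6.2 is written for the two Atrius stages, and 7.3.1b does not defer them. That contradicts the endpoints table, which says it covers the replication. In the second, the whole class, patients and outcome, is secondary. No text says so for the replication, and 7.3.1b says otherwise. Each reading needs a text change. The amendment log mentions a supplemental analysis plan for this trial that might settle the matter, but no separate text of it is among the documents available here.

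Four stronger readings are tempting, and the objection to each stands.

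- *All such patients count as successes.* A patient newly ordered a benzodiazepine or sedative hypnotic would not, and the no-action rule in 7.3.1b points to failure.
- *The primary estimate is wrong however they are scored.* Under failure scoring the relative risk is unchanged and power is only about 1, 2 and 5 points below the restricted analysis at f = 10%, 25% and 50%.
- *The power loss is far larger.* Leaving the correlation at 0.1 in the mixed set gives 25% (success) and 52% (failure) at f = 50%, but that credits fixed-outcome patients with between-provider variation they do not have. Losses would exceed the table if the share varied widely between providers.
- *About half the patients could be affected*, because expected Atrius numbers rise from 2000 to 4000 (4.3.2). Stage 2 admits patients on one anticholinergic, adds providers and has longer follow-up; the replication requires two different anticholinergics.

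For Stage 2, sections 3.2.2 and 7.3.1a already point anticholinergics to secondary analyses, so the conflict is not of the same strength there.

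**Conclusion.** The point holds for the replication trial: the eligibility and denominator rules conflict with the endpoints table, and the scoring of the affected patients is not settled. Under either scoring the absolute difference shrinks by the anticholinergic-only share. Success scoring also biases the relative risk toward 1 and costs about 4, 12 and 29 points of power against the restricted denominator at shares of 10%, 25% and 50%; failure scoring costs little. These sizes rest on an assumed cluster size, usual-care rate and share, none of them stated for the replication, so they are illustrations and not estimates of the actual loss. The plan should be corrected before outcomes are compared by arm, because a denominator chosen afterwards would be post hoc.

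**What to change.** In 7.3.1b, restrict the primary denominator to patients with a visit who qualify on at least 90 pills of a benzodiazepine or sedative hypnotic. Analyse anticholinergic-only patients in the secondary analysis that adds anticholinergic discontinuation to the outcome. If the intent is instead that anticholinergics count in the replication primary outcome, correct the endpoints table and define the replication outcome accordingly. For Stage 2, state the same restriction in 7.3.1a, to confirm what sections 3.2.2 and 7.3.1a already imply.

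Cost: one sentence in each place and a somewhat smaller primary denominator. No new data are needed. In the illustration, restricting gives at least as much power as either default scoring at every share shown.
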